## **7.4 Demographic and Baseline Characteristics**

### **7.4.1 Demography and Physical Characteristics**

Demographics and baseline characteristics variables that are listed in [Section 6.1](#) will be summarized by treatment and all data will be provided in listings. Continuous baseline parameters (such as age, height, weight, BMI, facial inflammatory lesion counts, facial noninflammatory lesion counts, and DLQI/CDLQI total score), facial IGA, Truncal PGA, PGI-S, and SSQ will be summarized descriptively using mean, median, SD, minimum, maximum, first quartile, and third quartile. For categorical baseline and demographic parameters (such as age group, country, reproductive status, sex, ethnicity, race, smoking history, facial IGA, Truncal PGA, PGI-S, and SSQ), frequencies and percentages of subjects will be provided; baseline facial IGA will be reported by individual Grade 3 or 4.

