#### **7.5.2.7 Change from Baseline in Facial IGA at Each Visit**

Change from baseline in facial IGA at each visit will be analyzed using a similar MMRM model as specified for the primary endpoint. The MMRM model will include treatment, visit, and treatment by visit interaction as categorical covariates and baseline facial IGA score as the only continuous variable. An unstructured correlation (UN) matrix will be used to model correlation within a subject; if convergence is an issue, a Toeplitz structure may be considered.

In addition, the following exploratory analyses will be performed:

- Change from baseline in facial IGA will be summarized in shift tables. In the shift table, for each treatment, the counts and percentages will be shown for baseline values crossed with each post-baseline timepoint. Agreement between the baseline score and each post-baseline score will be estimated with a weighted Kappa coefficient and corresponding 90% CI. A test of treatment difference for agreement will consist of a CMH test (ANOVA of row means) applied to a  $2 \times 3 \times 5$  Table (Baseline IGA facial strata  $\times$  treatment  $\times$  agreement score), where the agreement score is the Cicchetti-Allison weight used for the weighted Kappa coefficient, which is  $1 - |\text{difference}|/4$  for a 5 point score such as the facial IGA, so the value is =1 if there is perfect agreement,  $\frac{3}{4}$  if the scores are one category apart (in either direction),  $\frac{1}{2}$  if 2 apart,  $\frac{1}{4}$  if 3 apart and 0 if 4 apart. The latter score can happen only if baseline score is 4 and post-baseline score is 0.
- Change from baseline in facial IGA at Week 12 will be analyzed using an ordinal logistic regression model with treatment, facial IGA score at baseline (Grade 3 vs. 4) as categorical covariates. Odds ratios resulting from this model along with 90% CI will be reported.

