### **7.5.3 Exploratory Efficacy Analyses**

The continuous data endpoints of change and percent change from baseline will be analyzed using the MMRM approach as described for the primary efficacy analysis in [Section 7.5.1](#). Summary statistics and the results of statistical testing at each visit will be provided for each continuous exploratory variable. In addition, the change from baseline in PGI-S and Truncal PGA (by body region as well as the overall and the worst score across three regions) will be summarized and analyzed by shift tables and ordinal logistic regressions as described in [Section 7.5.2.7](#). Baseline of the response variable will be added to the ordinal logistic regression model as a categorical variable. The overall Truncal PGA will be presented separately for all subjects, adolescents, and adults.

The frequency and percentage of subjects for subjects for categorical exploratory endpoints related to Truncal PGA (by body region as well as the overall and the worst score across three regions), facial IGA, PGI-C, PGI-S, SSQ, and SSRS will be summarized at each protocol-specified visit. For proportion of subjects in each response category for the SSQ and SSRS, the difference in distribution between each dose of imidolimab and placebo will be analyzed using the approach described for the proportion of subjects in each response category for the PGI-C in [Section 7.5.2.9](#). For other categorical exploratory endpoints, an unadjusted risk difference and 90% exact unconditional CIs will be estimated between each dose of imidolimab and placebo for all subjects and within each stratum for facial IGA at baseline (Grade 3 vs. 4); the common risk difference will also be tested using a generalized CMH test as described in [Section 7.5.2.8](#).

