Logistic Regression with GEE using PROC GENMOD	<pre> PROC GENMOD DESCENDING;   CLASS SUBJECT TRT VISIT BASE;   MODEL Y= BASE TRT VISIT / LINK=LOGIT DIST=BIN;   REPEATED SUBJECT=SUBJECT / TYPE=UN;   LSMEANS TRT VISIT / DIFF CL ALPHA=0.1;   ODS OUTPUT LSMEANDIFFS = LSDIFS ESTIMATES=EST LSMEANS=LSMEANS PARAMETERESTIMATES=PE; RUN; Where TRT is treatment, VISIT is the study visit number, and BASE is the baseline of outcome variable. </pre>
Ordinal Logistic Regression using PROC LOGISTIC	<pre> PROC LOGISTIC;   CLASS TRT BASE BASEFIGA;   MODEL Y = TRT BASE BASEFIGA; RUN; Where Y is the ordinal outcome variable, TRT is treatment, BASEFIGA is the facial IGA score at baseline, BASE the baseline of outcome variable. Remove BASEFIGA from the model if outcome variable is facial IGA. </pre>

Test	Template SAS Code for Modeling (SAS Version 9.4)
Cochran-Mantel-Haenszel ANOVA statistics (row means score)	<pre>PROC FREQ;   TABLES BASEFIGA*TRT*X/CMH2 ALPHA=0.1; RUN; </pre> 
Where BASEFIGA is facial IGA at baseline, TRT is treatment, and X is the outcome variable.

Exact unconditional CI	<pre>PROC FREQ;   TABLES TRT*X/ RISKDIFF(CL=EXACT) ALPHA=0.1;   EXACT RISKDIFF; RUN; </pre> 
Where TRT is treatment, and X is the outcome variable.

Obtaining generalized risk difference	<pre>PROC FREQ;   TABLES TRT*X / ALL LIST MISSING ALPHA=0.1;   TEST SMDCR; RUN; </pre> 
Where TRT is treatment, and X is the outcome variable.

Weighted Kappa and confidence interval	<pre>PROC FREQ;   WEIGHT COUNT;   TABLES BASEFIGA*TRT*X/AGREE ALPHA=0.1; RUN; </pre> 
Where BASEFIGA is facial IGA at baseline, TRT is treatment, and X is the outcome variable.

Test of treatment difference for agreement	<pre>PROC FREQ;   TABLES BASEFIGA*TRT*X/CMH2; RUN; </pre> 
Where BASEFIGA is facial IGA at baseline, TRT is treatment, and X is the Cicchetti-Allison weight of outcome variable. Cicchetti-Allison weight = 1-abs(CHG)/(k-1), where k = number of categories of the outcome variable.

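### The Appendix 2 weighted-kappa template crosses treatment with outcome, so it cannot give the baseline-to-visit agreement in facial IGA that SAP 7.5.2.7 specifies (minor, exploratory only)

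*SAP*

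**What the plan says.** SAP 7.5.2.7 describes a shift table for facial IGA, built for each treatment, with baseline grade against the grade at each post-baseline visit. It then says: "Agreement between the baseline score and each post-baseline score will be estimated with a weighted Kappa coefficient", with a 90% CI. Separately, it plans a CMH test of treatment difference, laid out as baseline stratum by treatment by agreement score. The agreement score is the Cicchetti-Allison weight.

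The Appendix 2 template for the weighted kappa is "TABLES BASEFIGA*TRT*X/AGREE ALPHA=0.1". Its legend reads: "Where BASEFIGA is facial IGA at baseline, TRT is treatment, and X is the outcome variable".

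Two other templates in that appendix help to interpret it. The general CMH template has the same table request with a different option: "TABLES BASEFIGA*TRT*X/CMH2 ALPHA=0.1". The template that tests treatment difference in agreement defines its outcome from change from baseline: "Cicchetti-Allison weight = 1-abs(CHG)/(k-1), where k = number of categories of the outcome variable".

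On the baseline range, SAP 7.4.1 says that "baseline facial IGA will be reported by individual Grade 3 or 4", which matches the eligibility criteria.

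**The concern.** The text and the code describe different tables. The text wants baseline against visit score, one table per arm. The code makes treatment against visit score, one table per baseline grade. An agreement statistic compares the row variable with the column variable, so in the code it would compare the arm a subject was in with the grade the subject reached.

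A programmer who follows the template would get no kappa, or a number that says nothing about change from baseline. The second outcome is the worse one, because a missing statistic is usually noticed and a plausible-looking one may not be.

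**Working it through.** The reading of the code rests on SAS syntax, which the documents do not state. In a PROC FREQ request A\*B\*C, the last two variables form the row and column and the first is the stratum. AGREE gives kappa only for a square table.

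**1. The plan's own weights.** For a 5-point score the weight is 1 - |d|/(k - 1) with k = 5. For d = 0, 1, 2, 3, 4 this gives 1, 0.75, 0.5, 0.25, 0, as in SAP 7.5.2.7.

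**2. What the text requires.** There are three arms and five post-baseline visits (Weeks 2, 4, 8, 12, 20), so 3 x 5 = 15 kappas. Each comes from a table of baseline grade by visit grade on the 0-4 scale.

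**3. What the template forms.** At each visit it makes one table per baseline grade, so two tables and none for a single arm. Each has three rows (arms) and up to five columns (grades). It is square only if the table has exactly three grade columns.

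**4. Why it cannot give the specified quantity.** Baseline is constant within each stratum, and neither the row nor the column carries it. Two limiting cases show the consequence.
- If the arms have identical outcome distributions, each cell proportion equals row margin times column margin. Observed and expected agreement are then equal and kappa is 0, however much or little subjects changed.
- If nobody changes, the intended kappa is 1. The template table then has three rows and one occupied column in each stratum, so it is not square.

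**5. Illustration.** The documents contain no shift data, so these counts are assumed: 40 per arm, 32 at baseline grade 3 and 8 at grade 4.
- From grade 3, numbers at visit grades 1/2/3: higher dose 6/12/14, lower dose 4/10/18, placebo 2/8/22.
- From grade 4, numbers at visit grades 2/3/4: higher dose 3/3/2, lower dose 2/4/2, placebo 1/4/3.

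Kappa = (Po - Pe)/(1 - Pe), where Po and Pe are weighted observed and expected agreement. The intended 5x5 table per arm gives:
- Higher dose: (0.79375 - 0.77375)/(1 - 0.77375) = 0.088
- Lower dose: (0.8375 - 0.8175)/(1 - 0.8175) = 0.110
- Placebo: (0.8875 - 0.8575)/(1 - 0.8575) = 0.211

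As an example for the higher dose, Po = (6 x 0.5 + 12 x 0.75 + 14 x 1 + 3 x 0.5 + 3 x 0.75 + 2 x 1)/40 = 31.75/40 = 0.79375.

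**6. Dependence on arm order.** Take the grade 4 subjects above as a 3x3 table of arm by visit grade, with weights 1, 0.5, 0. With arms ordered higher, lower, placebo, Po = 15.5/24 = 0.6458, Pe = 0.5764 and kappa = 0.164. With the order reversed, Po = 12.5/24 = 0.5208, Pe is unchanged and kappa = -0.131. The data are the same and the sign changes. This is a hand calculation on a table assumed to be trimmed to three grades, not a prediction of SAS output.

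**7. What the repair needs.** Swapping the variables is not enough. Baseline facial IGA takes only grades 3 and 4, so baseline by visit is at most 2x5 unless zero-count cells for the missing grades are kept. Adding them does not change kappa, because the factor 1/(k - 1) cancels between numerator and denominator. They only make the table square.

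**The case against.** Appendix 2 says of itself that it will be completed before the SAP is signed off, and its code is labelled as template. The wording of 7.5.2.7 is unambiguous and writes out the weights, so an alert programmer would follow the text. The mock-up tables are in a separate document that may show the right layout. The analysis is exploratory, and no decision or error rate rests on it. All of this stands and sets the weight of the point. It does not reconcile the code with the text.

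A loss in text extraction is not a likely explanation. The asterisks are intact and the legend defines each variable in words. The identical request in the CMH template, where treatment by outcome is the right layout, suggests a copied line, but that is inference.

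Three stronger readings are tempting, and the documents do not support them.

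- A reader might count many more affected kappas, because SAP 7.5.3 refers PGI-S and the Truncal PGA scores back to 7.5.2.7 with these words: "will be summarized and analyzed by shift tables and ordinal logistic regressions as described in". That sentence names shift tables and ordinal logistic regression and does not mention kappa. Only the 15 for facial IGA follow directly from the text.
- A reader might infer that the template yields a particular wrong value. That depends on which grades occur, and on whether the software trims each stratum to its own grades. The documents settle neither. How far the value moves when the arms are reordered depends on the counts; only the dependence on order is general.
- A reader might infer that this is the only place where Appendix 2 departs from the text. The comparison here covers only the two agreement templates. Of those, the one for the treatment-difference test does use change from baseline, and the kappa template does not.

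**Conclusion.** The point holds: the kappa template is wrong as written and cannot return the agreement that SAP 7.5.2.7 specifies, however TRT or X is coded within the legend's definitions. It is minor. It affects 15 exploratory facial IGA kappas and their 90% CIs. The primary MMRM, the sample size and the stated 80% power are unaffected.

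The conclusion that the rows and columns are the wrong variables rests on how PROC FREQ reads a three-way request. The conclusion that kappa is often absent rests on the square-table condition. The numerical illustrations use assumed counts and indicate no expected result.

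**What to change.** Replace the template request, run by visit, with `TABLES TRT*(baseline score)*(post-baseline score) / AGREE ALPHA=0.1`. Use `WEIGHT COUNT / ZEROS` and supply zero-count cells for unobserved grades, so that each facial IGA table is 5x5. Rewrite the legend to name treatment as the stratum, the baseline score as the row and the post-baseline score as the column.

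State in SAP 7.5.3 whether the kappa is also wanted for PGI-S and Truncal PGA. If so, use each outcome's own baseline score, which the current template does not contain: 4x4 for PGI-S and 5x5 for each Truncal PGA score.

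The cost is a few lines of template code, one legend and, if wanted, one clarifying sentence before SAP sign-off. It needs no additional subjects and no protocol amendment.

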### **13. APPENDIX 3 MOCKUP TABLES, LISTINGS, AND GRAPHS (TLGs)**

Mockup tables, listings, and graphs are presented in a separate document.
